5.3 Randomization and Blinding

This study follows a randomized, double-blind, placebo-controlled design. Patients in Part A will be randomized via the Interactive Response Technology (IRT) system to 1 of 4 parallel treatment groups on Day 1 in a 1:1:1:1 ratio. However, prerandomization will occur within the IRT system at least 7 days prior to randomization. Patients in Part B will be randomized via the IRT system to 1 of 3 parallel treatment groups on Day 1 in a 1:1:1 ratio. Prerandomization is not applicable in Part B.

Both EYP001a and placebo will be provided as tablets for oral administration and will be identical in appearance.

Prerandomization/randomization information will be concealed from the Investigators and the patients until the end of the study, with the exception of an emergency situation involving a patient that required unblinding of the treatment assignment.

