10.2.8 Sample Size Determination

The sample size of 114 randomized patients (n = 24 patients in Part A and n = 90 in Part B [n = 30 patients per treatment group]) is based on the efficacy endpoint: absolute change in LFC as measured by MRI-PDFF from baseline to Week 12, assuming that the treatment difference between each active treatment group with placebo is at least 5.1% with a common standard deviation of 5.8%.

With a 2-sample Z-test with the power of 0.8 and an overall family-wise 1-sided alpha of 0.025 (or each active versus placebo alpha = 0.0125 after Bonferroni adjustment), 26 patients per treatment group will be needed to complete the Week 12 Visit. With the consideration of an approximately 13% dropout rate before Week 12, 30 patients will be randomized per treatment group in Part B.

A Lan-DeMets alpha spending function will be used for this group sequential design. Nonbinding O'Brien-Fleming efficacy boundaries and futility boundaries will be calculated using EAST 6.4 software. The efficacy and futility boundaries are described in [Table 6](#).

At the time of the interim analysis, if the test-statistic is equal to or less than the futility boundary, the Sponsor can decide to stop the study due to lack of efficacy.

Table 6. Efficacy and Futility Boundaries for Part B

Look	Week 8 Number of Patients	Week 12 Number of Patients	Information Fraction	Cumulative Alpha Spent	Cumulative Beta Spent	Z Efficacy Boundary	Z Futility Boundary	p-value Efficacy Boundary	p-value Futility Boundary
#1 (interim analysis)	45	23	0.25	<0.0001	0.0113	-4.7604	0.6966	<0.0001	0.7570
#2 (final analysis)	90		1	0.0125	0.1962	-2.2414	-2.2414	0.0125	0.0125

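### The Part B interim futility rule has its inequality reversed: as worded, it permits stopping for lack of efficacy on every favourable result

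*Protocol*

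**What the plan says.** Protocol section 10.2.8 describes a two-look group sequential design for Part B: "Nonbinding O'Brien-Fleming efficacy boundaries and futility boundaries will be calculated using EAST 6.4 software". The decision rule is that, at the interim, "if the test-statistic is equal to or less than the futility boundary, the Sponsor can decide to stop the study" for lack of efficacy.

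Table 6 in the same section gives:

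| Look | Z efficacy | Z futility | p efficacy | p futility | Cumulative beta |
|---|---|---|---|---|---|
| Interim (information fraction 0.25) | -4.7604 | 0.6966 | <0.0001 | 0.7570 | 0.0113 |
| Final | -2.2414 | -2.2414 | 0.0125 | 0.0125 | 0.1962 |

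The planning values are a treatment difference of "at least 5.1% with a common standard deviation of 5.8" percent, "power of 0.8 and an overall family-wise 1-sided alpha of 0.025 (or each active versus placebo alpha = 0.0125 after Bonferroni adjustment"), and "26 patients per treatment group will be needed to complete the Week 12 Visit".

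SAP section 3.1.5 defines change as the visit value minus baseline, so a fall in liver fat is negative. SAP section 2.2.4 repeats the sample size without the boundaries. SAP section 4.1 refers to a separate Interim Analysis Plan for interim details.

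**The concern.** Both efficacy bounds are negative, so a more negative Z is better for EYP001a. A futility bound of +0.6966 should then flag results at or above it. The sentence flags results at or below it. A result past the efficacy bound, Z <= -4.7604, would count as overwhelming efficacy and as futility at once.

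At stake is a stopping rule on the primary endpoint that permits stopping when the drug works. The power and the beta spending in Table 6 do not describe the rule as worded. In the documents supplied, this sentence is the only statement of how the futility bound is to be used.

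A smaller point is that the sentence speaks of one test statistic, while Part B has two dose-versus-placebo comparisons.

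**Working it through.** **Inputs** (Protocol 10.2.8 and Table 6): difference 5.1, SD 5.8, one-sided alpha 0.0125 per comparison, power 0.8, 26 completers per group, information fraction t = 0.25, and the boundaries above. Allocation is 1:1:1 (Protocol 5.3).

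**1. Sample size.** n = 2 × (5.8/5.1)² × (2.2414 + 0.8416)² = 2 × 1.2933 × 9.505 = 24.6, so 25 per group. The plan says 26, which is close. 26/(1 - 0.13) = 29.9, so 30 randomized, as stated.

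**2. Which tail the p-values use.** Phi(-2.2414) = 0.0125 and Phi(0.6966) = 0.7570, both as printed. The p-values are lower-tail probabilities: small p and negative Z mean benefit, large p and positive Z mean the opposite.

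**3. Efficacy bound.** Lan-DeMets O'Brien-Fleming spending is 2 × [1 - Phi(z(1 - a/2)/√t)]. With a = 0.0125, t = 0.26 gives Z = -4.7604, the printed value; t = 0.25 gives -4.860. The printed 0.25 therefore appears to stand for 0.26. This does not affect the direction of the rule.

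**4. Interim drift under the planned effect.** Drift = -(5.1/5.8) × √(n/2) × √t.
- n = 26, t = 0.25: -0.8793 × 3.6056 × 0.5 = -1.585.
- n = 25, t = 0.26: -0.8793 × 3.5355 × 0.5099 = -1.585.

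**5. Which direction reproduces Table 6.**
- P(Z >= 0.6966 | planned effect) = 1 - Phi(0.6966 + 1.585) = 0.0113, the printed interim beta.
- Two-look power by numerical integration (joint normal, correlation √t), stopping for futility if Z >= 0.6966: with n = 25 and t = 0.26 it is 0.8038, so the type II error is 0.1962, the printed cumulative beta. With n = 26 and t = 0.25, power is 0.820.

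Both printed betas follow from an upper-tail futility rule.

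**6. The rule as written against the rule intended.**

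| Quantity | Stop if Z <= 0.6966 (written) | Stop if Z >= 0.6966 (intended) |
|---|---|---|
| P(triggered), planned effect, n = 26, t = 0.25 | 0.9887 | 0.0113 |
| Same, n = 25 to 26, t = 0.25 to 0.26 | 0.988 to 0.990 | 0.010 to 0.012 |
| P(triggered), no effect | 0.757 | 0.243 |
| Power if always obeyed, efficacy checked first | about 0.004 | 0.80 to 0.82 |

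The expected interim Z if the drug works as planned, about -1.59, lies inside the written stopping region.

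**7. On the liver-fat scale.** At n × t = 6.5 patients per group, the standard error of the difference is 5.8 × √(2/6.5) = 3.22, and 0.6966 × 3.22 = 2.24. As written, the rule is triggered unless EYP001a is more than about 2.2 percentage points worse than placebo.

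**8. Readings that might rescue the sentence.** Taking placebo minus active would make the efficacy bounds positive, and they are printed negative. A minus sign lost from 0.6966 would give p = 0.243, not 0.7570. On the p-value scale, p <= 0.7570 is the same region as Z <= 0.6966.

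**The case against.** The strongest reply is about consequence. The bounds are nonbinding and the Sponsor only may stop, so 98.8 to 99.0% is the chance that a permission is triggered, not the chance that the trial stops. Type I error is not inflated: the final bound of -2.2414 uses the full 0.0125, and extra futility stopping can only lower it. A competent analyst with Table 6 in hand would see what was meant. The Part B interim was completed in February 2021 (SAP 4.1), and SAP 4.2 still plans the Week 12 database lock, so nothing supplied suggests a stop on the wrong side. The operative rule may be correct in the Interim Analysis Plan or the DSMC charter, neither of which was supplied.

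All of this stands as a limit on the practical harm. It does not make the sentence right: a permissive rule still has to name the results that permit stopping, and this one names the favourable ones. Neither the protocol nor the SAP corrects it elsewhere.

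On the single test statistic, the reply is partly right: Table 6 uses 0.0125, so its bounds are already per comparison. What stays open is whether one dose or both must cross before the study may stop.

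**Conclusion.** The concern holds. The futility sentence contradicts its own table, and the table is the correct one. Under the planned effect the written rule is triggered with probability 98.8 to 99.0% instead of about 1.1%; with no effect, 75.7% instead of 24.3%. Obeyed literally, it would cut power from about 0.80 to about 0.004.

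These figures assume the protocol's difference of 5.1 and SD of 5.8, 25 to 26 completers per group and an information fraction of 0.25 to 0.26. With 30 per group at t = 0.25, the 98.9% becomes 99.2%. The direction of the error depends on none of these assumptions.

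This is an error in the stated decision rule. The boundaries, beta spending and sample size are unaffected, and it is not evidence that the interim decision was wrong. It should be corrected because it reverses a stopping threshold on the primary endpoint.

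**What to change.** - Reword the rule in Protocol 10.2.8 along these lines: *with Z computed as EYP001a minus placebo, so that negative values favour EYP001a, the Sponsor may stop for lack of efficacy if the interim Z is at or above the futility bound (Z >= 0.6966, one-sided p >= 0.7570).*
- State that the bound is applied to each dose-versus-placebo comparison, and whether one or both must cross before the study as a whole may stop.
- Check the Interim Analysis Plan and the DSMC charter for the same sentence and correct it there if present.
- Because the interim is complete, record in the clinical study report which direction was applied in February 2021.

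The cost is a sentence or two in the protocol, or a note to file, and one statement in the report. Boundaries, sample size and conduct do not change.

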11 DATA MANAGEMENT AND RECORD KEEPING

11.1 Data Management

11.1.1 Data Handling

Data will be recorded at the clinical site on eCRFs and reviewed by the Clinical Research Associate (CRA) during monitoring visits. The CRAs will verify data recorded in the EDC system with source documents for completeness and accuracy. Data reported in the eCRFs that are derived from source documents should be consistent with the source documents or the discrepancies should be explained. All corrections or changes made to any study data in the EDC system will be appropriately tracked in an audit trail. An eCRF will be considered complete when all missing, incorrect, and/or inconsistent data has been accounted for.

11.1.2 Computer Systems

Data will be processed using a validated computer system that adheres to Title 21 of the US Code of Federal Regulations (21 CFR Part 11) compliance.

11.1.3 Data Entry

Data must be recorded using the EDC system as the study is in progress. All clinical site personnel must log into the system using their secure user name and password in order to enter, review, or correct study data. These procedures must comply with 21 CFR Part 11 and other appropriate international regulations. All passwords will be strictly confidential.

11.1.4 Medical Information Coding

For medical information, the latest versions of the following thesauri will be used:

- MedDRA for medical history and adverse events
- WHO Drug Dictionary for prior and concomitant medications

11.1.5 Data Validation

Validation checks programmed within the EDC system, as well as supplemental validation performed via review of the downloaded data, will be applied to the data in order to ensure accurate, consistent, and reliable data. Data identified as erroneous, or data that are missing, will be referred to the clinical site for resolution through data queries.

The eCRFs must be reviewed and electronically signed by the Investigator.

11.2 Record Keeping

Records of patients, source documents, monitoring visit logs, eCRFs, inventory of study drug, regulatory documents, and other Sponsor correspondence pertaining to the study must be kept in the appropriate study files at the clinical site. Source data is defined as all information in original records and certified copies of original records of clinical findings, observations, or other activities in a clinical study necessary for the evaluation and reconstruction of the clinical study. Source data are contained in source documents (original records or certified copies). These records will be retained in a secure file for the period as set forth in the Clinical Study Agreement. Prior to transfer

or destruction of these records, the Sponsor must be notified in writing and be given the opportunity to further store such records.

11.3 End of Study

The end of the study (“study completion”) is defined as the date of the last protocol-specified visit/assessment (including telephone contact) for the last patient in the study.

12 INVESTIGATOR REQUIREMENTS AND QUALITY CONTROL

12.1 Ethical Conduct of the Study

Good Clinical Practice (GCP) is an international ethical and scientific quality standard for designing, conducting, recording, and reporting studies that involve human patients. Compliance with this standard provides public assurance that the rights, safety, and well-being of study patients are protected, consistent with the principles that have their origin in the Declaration of Helsinki, and that the clinical study data are credible.

12.2 Institutional Review Board/Independent Ethics Committee

The Institutional Review Board (IRB)/Independent Ethics Committee (IEC) will review all appropriate study documentation in order to safeguard the rights, safety, and well-being of patients. The study will only be conducted at clinical sites where IRB/IEC approval has been obtained. The protocol, Investigator's Brochure, ICF, advertisements (if applicable), written information given to the patients, safety updates, annual progress reports, and any revisions to these documents will be provided to the IRB/IEC by the Investigator.

Federal regulations and ICH Guidelines require that approval be obtained from an IRB/IEC prior to participation of patients in research studies. Prior to study onset, the protocol, any protocol amendments, ICFs, advertisements to be used for patient recruitment, and any other written information regarding this study to be provided to a patient or patient's legal guardian must be approved by the IRB/IEC.

No drug will be released to a clinical site for dosing until written IRB/IEC authorization has been received by the Sponsor.

12.3 Informed Consent

The ICF and any changes to the ICF made during the course of the study must be agreed to by the Sponsor or designee and the IRB/IEC prior to its use and must be in compliance with all ICH GCP, local regulatory requirements, and legal requirements.

The Investigator must ensure that each study patient is fully informed about the nature and objectives of the study and possible risks associated with participation and must ensure that the patient has been informed of his/her rights to privacy. The Investigator or designee (where locally permitted) will obtain written informed consent from each patient before any study-specific activity is performed and should document in the source documentation that consent was obtained prior to enrollment in the study. The original signed copy of the ICF must be maintained by the Investigator and is subject to inspection by a representative of the Sponsor, their representatives, auditors, the IRB/IEC and/or regulatory agencies. A copy of the signed ICF will be given to the patient.

12.4 Patient Card

On enrollment in the study, the patient will receive a patient card to be carried at all times. The patient card will state that the patient is participating in a clinical research study and contact details in case of an emergency.

12.5 Study Monitoring Requirements

It is the responsibility of the Investigator to ensure that the study is conducted in accordance with the protocol, Declaration of Helsinki, ICH GCP, and applicable regulatory requirements, and that valid data are entered into the eCRFs.

It is the responsibility of the Investigator to ensure that the study is conducted in accordance with the protocol, ICH GCP, Directive 2001/20/EC for clinical sites in the European Union, applicable regulatory requirements, and the Declaration of Helsinki and that valid data are entered into the eCRFs.

To achieve this objective, the monitor's duties are to aid the Investigator and, at the same time, the Sponsor in the maintenance of complete, legible, well organized and easily retrievable data. Before the enrollment of any patient in this study, the Sponsor or their designee will review with the Investigator and clinical site personnel the following documents: protocol, Investigator's Brochure, eCRFs and procedures for their completion, informed consent process, and the procedure for reporting SAEs.

The Investigator will permit the Sponsor or their designee to monitor the study as frequently as deemed necessary to determine that data recording and protocol adherence are satisfactory. During the monitoring visits, information recorded on the eCRFs will be verified against source documents and requests for clarification or correction may be made. After the eCRF data is entered by the clinical site, the CRA will review the data for safety information, completeness, accuracy, and logical consistency. Computer programs that identify data inconsistencies may be used to help monitor the clinical study. If necessary, requests for clarification or correction will be sent to Investigators. The Investigator and his/her staff will be expected to cooperate with the monitor and provide any missing information, whenever possible.

All monitoring activities will be reported and archived. In addition, monitoring visits will be documented at the clinical site by signature and date on the study-specific monitoring log.

12.6 Disclosure of Data

Data generated by this study must be available for inspection by the FDA, the Sponsor or their designee, applicable foreign health authorities, and the IRB/IEC as appropriate. Patients or their legal representatives may request their medical information be given to their personal physician or other appropriate medical personnel responsible for their welfare.

Patient medical information obtained during the study is confidential and disclosure to third parties other than those noted above is prohibited.

12.7 Retention of Records

To enable evaluations and/or audits from regulatory authorities or the Sponsor, the Investigator will keep records, including the identity of all participating patients (sufficient information to link records, eg, eCRFs and hospital records), all original signed ICFs, copies of all eCRFs, SAE forms, source documents, and detailed records of treatment disposition. The records should be retained by the Investigator according to specifications in the ICH guidelines, local regulations, or as specified in the Clinical Study Agreement, whichever is longer. The Investigator must obtain written permission from the Sponsor before disposing of any records, even if retention requirements have been met.

If the Investigator relocates, retires, or for any reason withdraws from the study, the Sponsor should be prospectively notified. The study records must be transferred to an acceptable designee, such as another Investigator, another institution, or to the Sponsor.

12.8 Publication Policy

Following completion of the study, the data may be considered for publication in a scientific journal or for reporting at a scientific meeting. Each Investigator is obligated to keep data pertaining to the study confidential. The Investigator must consult with the Sponsor before any study data are submitted for publication. The Sponsor reserves the right to deny publication rights until mutual agreement on the content, format, interpretation of data in the manuscript, and journal selected for publication are achieved.

12.9 Financial Disclosure

Investigators are required to provide financial disclosure information to the Sponsor to permit the Sponsor to fulfill its obligations under US 21 CFR Part 54. In addition, Investigators must commit to promptly updating this information if any relevant changes occur during the study and for a period of 1 year after the completion of the study.

12.10 Insurance and Indemnity

In accordance with the relevant national regulations, the Sponsor has taken out patient liability insurance for all patients who give their consent to the clinical study.

12.11 Legal Aspects

The clinical study is submitted to the relevant national competent authorities in all participating countries to achieve a clinical trial authorization (CTA).

The study will commence (ie, initiation of study centers) when the CTA and favorable ethics opinion have been received.

13 STUDY ADMINISTRATIVE INFORMATION

13.1 Protocol Amendments

Any amendments to the study protocol will be communicated to the Investigators by the Sponsor or their designee. All protocol amendments will undergo the same review and approval process as the original protocol.

Written verification of IRB/IEC and Competent Authority approval will be obtained before any amendment is implemented that affects patient safety or the evaluation of safety, and/or efficacy. Modifications to the protocol that are administrative in nature do not require IRB/IEC and Competent Authority approvals; however, the IRB/IEC and Competent Authority will be notified about an administrative change if required by local regulations.

A protocol amendment may be implemented after it has been approved by the IRB/IEC and Competent Authority, unless immediate implementation of the change is necessary for patient safety. In this case, the situation must be documented and reported according to the local regulations.

APPENDIX A: SCHEDULE OF PROCEDURES

Table 7. Schedule of Procedures – Part A

Assessment	Screening [¶]	Treatment Period								EOS FUP Visit	ET Visit [¶]	
		Safety Run-In Period					Continued Treatment Period					
		Study Week -12 to -1	0	1	2	3	4	8	12	14		
Study Day [¶]	-84 to -3	Day 1	Day 7	Day 14	Day 21	Day 28	Day 56	Day 84	Day 98			
Informed consent	X											
Eligibility criteria	X	X [¶]										
Demographics	X											
Medical history	X											
Prior/concomitant medications [¶]	X	X	X	X	X	X	X	X	X	X		
Height and body weight [¶]	X	X	X	X	X	X	X	X	X	X		
BMI calculation [¶]	X	X	X	X	X	X	X	X	X	X		
Waist circumference [¶]	X	X	X	X	X	X	X	X	X	X		
Physical examination	X	X	X	X	X	X	X	X	X	X		
Vital signs [¶]	X	X	X	X	X	X	X	X	X	X		
AUDIT-C [¶]	X			X	X	X	X	X				
Randomization		X										
Pruritus assessment [¶]		X	X	X	X	X	X	X	X	X		
Adverse event monitoring	X	X	X	X	X	X	X	X	X	X		
Viral serology [¶]	X											
Chemistry, hematology, coagulation, and lipid and metabolic profile [¶]		X	X	X	X	X	X	X	X	X		
Urinalysis [¶]	X	X	X	X	X	X	X	X	X	X		
Pregnancy test [¶]	X	X	X	X	X	X	X	X	X	X		
12-Lead ECG [¶]	X		X	X	X	X	X	X	X	X		
FibroScan [¶]	X							X		X		
MRI-PDFF and cT1 imaging [¶]	X							X		X [¶]		
Diet/lifestyle counseling [¶]	X	X	X	X	X	X	X	X	X	X		
PD biomarker sampling [¶]		X		X		X	X	X	X	X	X [¶]	
Liver fibrosis and inflammation sampling [¶]			X	X		X	X	X		X	X	

Table 7. Schedule of Procedures – Part A (Continued)

	Screening ^a	Treatment Period							EOS FUP Visit	ET Visit ^c
		Safety Run-In Period					Continued Treatment Period			
Study Week	-12 to -1	0	1	2	3	4	8	12	14	
Study Day ^b	-84 to -3	Day 1	Day 7	Day 14	Day 21	Day 28	Day 56	Day 84	Day 98	
Assessment										
PK sampling ^d		X ^z	X	X ^z	X	X	X	X	X	X ^z
Blood sampling for plasma storage ^d		X					X	X	X	X
Dispense patient diary		X								
Dispense EYP001a or placebo		X ^{bl}		X ^{bb}		X	X			
Collect used/unused study drug and assess compliance				X		X	X	X		X

Blood sample collection will be prioritized starting with the safety sample. All blood samples should be collected while the patient is in a fasted state, defined as nothing by mouth except water for ≥6 hours. Additional details on fasting during PK and PD sampling are provided in [footnotes w](#) and [b](#), respectively.

- The Screening Period may be up to 12 weeks in duration. A patient who is first designated as a screen failure prior to being randomized may be rescreened upon Sponsor or designee approval. If the patient was screen failed after the MRI-PDFF was completed, the original MRI-PDFF scan may be utilized for rescreening, provided it was obtained within 1 month prior to rescreening. Patients will be prerandomized into the study once all eligibility criteria are confirmed.
- A ±3-day window is acceptable for all visits during the Treatment Period, except for Days 1 and 14 of Part A, when the window is ±1 day.
- Patients who discontinue early from the study for any reason prior to completion of the Treatment Period will be requested to return to the clinic for an ET Visit within a maximum of 48 hours after their last intake of study drug, regardless of how many days they participated in the study. Patients who discontinue early from the study for any reason after completion of the Treatment Period and before the EOS FUP Visit will be requested to return to the clinic for an ET Visit as soon as possible and no later than the planned EOS FUP Visit.
- Perform prior to dosing.
- Authorized medications per exception list and on a case-by-case basis, as documented by written approval from the Sponsor, are acceptable.
- Height assessed only at screening.
- Use screening height for BMI calculation.
- Measure the waist circumference at the end of several consecutive natural breaths, at a level parallel to the floor, midpoint between the top of the iliac crest and the lower margin of the last palpable rib in the mid axillary line. The tape should be placed around the abdomen at the level of this midway point and a reading taken when the tape is snug but does not compress the skin.
- A complete physical examination (including general appearance; eyes, ears, nose, and throat; head and neck; chest and lungs; cardiovascular; abdomen; musculoskeletal; lymphatic; dermatological; neurological systems; mental status; and extremities) will be performed at screening. Brief, symptom-directed physical examinations will be performed on Days 1, 7, 14, 21, 28, 56, 84, and at the EOS and ET Visits.
- Vital signs include systolic and diastolic blood pressure, heart rate, respiratory rate, and body temperature and will be performed with the patient in the sitting position after 5 minutes of rest and before any blood draws. Clinical site staff will use a mercury sphygmomanometer or automatic blood pressure device with an appropriately sized cuff with the bladder centered over the brachial artery. Clinical site staff will record the arm used for the measurement and use the same arm throughout the study. Clinical site staff will measure and record the blood pressure. Blood pressure will be recorded to the nearest 2 mmHg mark on the manometer or to the nearest whole number on an automatic device. A blood pressure reading will be repeated 1 to 2 minutes later, and the second reading will also be recorded to the nearest 2 mmHg mark.
- Patients with AUDIT-C scores ≥3 points at screening will receive the full AUDIT and will be excluded if they score ≥8 points on the full AUDIT. Patients with AUDIT-C scores <3 points will not receive the full AUDIT.
- Can occur after eligibility check on Day -3 at the earliest and prior to dosing on Day 1 at the latest.

- m. Assess using a visual analog scale and 5-D questionnaire (degree, duration, direction, disability, and distribution) itch scale.
- n. Anti-HCV, anti-HIV, and anti-HBV status will be assessed, and HCV RNA will be reflexively tested. Samples will be collected for central laboratory analysis except if viral serology data is already available in patient's medical history/records and obtained within 90 days prior to screening.
- o. Collected after ≥ 6 hours of fasting. See [Appendix B](#) for the complete list of clinical laboratory parameters.
- p. Urinalysis will be evaluated from samples collected after ≥ 6 hours of fasting. Further analysis of urine sediment or urine microscopy will be performed when there are any abnormalities on any of the following 3 dipstick results: leukocyte esterase, blood, or nitrite, and if judged clinically significant by the Investigator.
- q. For women of childbearing potential, a serum hCG test will be performed at screening and the EOS and ET Visits. Urine hCG testing will be performed at all other visits. If a urine hCG test is positive, a serum hCG test will be performed. Follicle-stimulating hormone level will be measured at screening to confirm postmenopausal state in women ≤ 55 years of age.
- r. Single 12-lead ECGs will be performed at screening; on Days 7, 14, 21, 28, 56, and 84; and at the EOS and ET Visits after the patient has been resting in the supine position for at least 10 minutes. In case of evident bad quality of the tracing (eg, muscle tremor), the ECG will be repeated. QT interval corrected for heart rate using Fridericia's formula will be measured.
- s. FibroScan with the use of a probe appropriate for the patient's stature for VCTE assessment of LSM for fibrosis and CAP for steatosis with cut-off values LSM ≥ 8.5 kPa and CAP >300 dB/m, respectively. Patients do not need to undergo a CAP assessment if their medical records indicate an MRI-PDFF LFC $\geq 10\%$ within the 12 months prior to screening. Assessments at Day 84 and ET Visits are optional.
- t. Perform if FibroScan values (LSM and CAP) are within eligibility range; MRI-PDFF using standardized imaging acquisition calibration protocol and central reading to be performed at screening (as baseline value) and Week 12 or ET.
- u. Perform only for patients on study drug for ≥ 4 weeks.
- v. Diet/lifestyle counseling will occur as per standard of care at each study visit. High-level dietary and physical activity guidelines will be provided and documented in the eCRF.
- w. Intense PD sampling will occur on Day 1 (± 1 day) and Day 14 (± 1 day) of Part A at the following timepoints: 0 (predose, fasting), 4 (fasting), 6, 10, 12, and 24 hours postdose. Sparse PD sampling will also occur predose (fasting) and 2 hours postdose at the following visits: Days 28, 56, and 84. A sample will also be collected at the EOS and ET Visits. For BID dosing, PD sampling timepoints will be based on the time of morning dosing. Pharmacodynamic sampling will assess plasma levels of C4; FGF19; and total, primary, and secondary bile acids (such as CDCA, DCA, LCA, and/or others as appropriate).
- x. At the ET Visit (if applicable), a PK/PD sample should be collected, preferably within 24 to 48 hours of last intake of study drug. The date and time of the PK/PD draw and the last dose of study drug must be recorded in the eCRF.
- y. Liver fibrosis and inflammation parameters include ALT, AST, AST/ALT ratio, adiponectin, high sensitivity C-reactive protein, interleukin 6, tumor necrosis factor alpha, cytokeratin-18, fibronectin, hyaluronic acid, procollagen type III N-terminal peptide, tissue inhibitor of metalloproteinases-1 (and derived enhanced liver fibrosis score), Pro-C3, and chitinase-3-like protein 1 (also known as YKL-40).
- z. Intense PK sampling will occur on Day 1 (± 1 day) and Day 14 (± 1 day) of Part A at the following timepoints: 0 (predose), 1, 2, 4, 6, 8, 10, 12, and 24 hours postdose; samples will be collected in the fasted state predose to 4 hours postdose, inclusive. Sparse PK samples will be collected for all other visits. Plasma samples to assess trough concentrations of EYP001a will be collected predose (fasting) in the morning and 2 hours postdose (an optional sample may also be collected at 6 hours postdose) at the following visits: Days 7, 21, 28, 56, and 84. A sample will also be collected at the EOS and ET Visits. For BID dosing, PK timepoints will be based on the time of morning dosing.
 - aa. Plasma from blood samples will be stored for protocol-related safety testing or exploratory analyses.
 - bb. During intense PK/PD sampling on Days 1 and 14 of Part A, dosing will occur with water only; blood sampling timepoints are fixed during this period. The start of meal times must be captured and can vary with meal times in the morning and evening – limited up to 3 main meals per 24 hours with ± 2 -hour variability.

ALT = alanine aminotransferase; AST = aspartate aminotransferase; AUDIT = Alcohol Use Disorders Identification Test; AUDIT-C = Alcohol Use Disorders Identification Test-Concise; BID = twice daily; BMI = body mass index; C4 = 7 α hydroxy-4-cholesten-3-one; CAP = controlled attenuation parameter; CDCA = chenodeoxycholic acid; cT1 = iron-corrected T1; DCA = deoxycholic acid; ECG = electrocardiogram; eCRF = electronic case report form; EOS = End of Study; ET = Early Termination; FGF19 = fibroblast growth factor 19; FUP = Follow-up; HBV = hepatitis B virus; hCG = human chorionic gonadotropin; HCV = hepatitis C virus; HIV = human immunodeficiency virus; LCA = lithocholic acid; LFC = liver fat content; LSM = liver stiffness measurement; MRI-PDFF = magnetic resonance imaging proton density fat fraction; PD = pharmacodynamic; PK = pharmacokinetic; RNA = ribonucleic acid; VCTE = vibration-controlled transient elastography.

Table 8. Schedule of Procedures – Part B

	Screening ^a	Treatment Period								EOS FUP Visit	ET Visit ^b
		0	2	4	6	8	10	12	14		
Study Week	-12 to -1	Day 1	Day 14	Day 28	Day 42	Day 56	Day 70	Day 84	Day 98		
Study Day ^b	-84 to -3										
Assessment											
Informed consent	X										
Eligibility criteria	X	X ^b									
Demographics	X										
Medical history	X ^b										
Prior/concomitant medications ^b	X	X	X	X	X	X	X	X	X	X	
Height and body weight ^b	X	X	X	X		X		X	X	X	
BMI calculation ^b	X	X	X	X		X		X	X	X	
Waist and hip circumference ^b	X	X	X	X		X		X	X	X	
WHR and WHtR calculations ^b	X	X	X	X		X		X	X	X	
Physical examination ^b	X	X	X	X		X		X	X	X	
Vital signs ^b	X	X	X	X		X		X	X	X	
AUDIT-C ^b	X			X		X		X		X	
Randomization ^b		X									
Adverse event monitoring ^c	X	X	X	X	X	X	X	X	X	X	
Viral serology ^b	X										
Chemistry, hematology, and coagulation ^b	X	X	X	X	X ^b	X	X ^p	X	X	X	
Lipid and metabolic profile ^c	X	X	X	X		X		X	X	X	
Urinalysis ^b	X	X	X	X		X		X	X	X	
Pregnancy test ^b	X	X	X	X		X		X	X	X	
12-Lead ECG ^b	X		X	X		X		X	X	X	
FibroScan ^b	X							X		X	
MRI-PDFF and cT1 imaging ^b	X							X		X ^b	
Diet/lifestyle counseling ^b	X	X	X	X		X		X	X	X	
PD biomarker sampling ^b		X	X	X		X		X	X	X ^b	
Liver fibrosis and inflammation sampling ^b			X		X		X			X	X
PK sampling ^b		X	X	X		X		X	X	X ^y	

Table 8. Schedule of Procedures – Part B (Continued)

	Screening ^a	Treatment Period								EOS FUP Visit	ET Visit ^c
		-12 to -1	0	2	4	6	8	10	12	14	
Study Week	-84 to -3	Day 1	Day 14	Day 28	Day 42	Day 56	Day 70	Day 84	Day 98		
Assessment											
Blood sampling for plasma storage ^b	X	X	X	X		X		X	X	X	X
Dispense EYP001a or placebo		X	X	X	X	X	X	X			
Collect used/unused study drug and assess compliance			X ^{cc}	X ^{cc}	X	X ^{cc}	X ^{cc}	X ^{cc}		X	
Blood sample collection will be prioritized starting with the safety sample. All blood samples should be collected while the patient is in a fasted state, defined as nothing by mouth except water for ≥6 hours.											
a.	The Screening Period may be up to 12 weeks in duration. A patient who is first designated as a screen failure prior to being randomized may be rescreened upon Sponsor or designee approval. If the patient was screen failed after the MRI-PDFF was completed, the original MRI-PDFF scan may be utilized for rescreening, provided it was obtained within 1 month prior to rescreening.										
b.	A ±3-day window is acceptable for all visits during the Treatment Period.										
c.	Patients who discontinue early from the study for any reason prior to completion of the Treatment Period will be requested to return to the clinic for an ET Visit within a maximum of 48 hours after their last intake of study drug, regardless of how many days they participated in the study. Patients who discontinue early from the study for any reason after completion of the Treatment Period and before the EOS FUP Visit will be requested to return to the clinic for an ET Visit as soon as possible and no later than the planned EOS FUP Visit.										
d.	Perform prior to dosing.										
e.	If pruritus is reported, assess using a visual analog scale and 5-D questionnaire (degree, duration, direction, disability, and distribution) itch scale.										
f.	Authorized medications per exception list and on a case-by-case basis, as documented by written approval from the Sponsor, are acceptable.										
g.	Height assessed only at screening.										
h.	Use screening height for BMI and WHtR calculations.										
i.	Measure the waist circumference at the end of several consecutive natural breaths, at a level parallel to the floor, midpoint between the top of the iliac crest and the lower margin of the last palpable rib in the mid axillary line. The tape should be placed around the abdomen at the level of this midway point and a reading taken when the tape is snug but does not compress the skin. Measure the hip circumference at a level parallel to the floor, at the largest circumference of the buttocks. The tape should be placed around the hips and a reading taken when the tape is snug but does not compress the skin. Waist to hip ratio (WHR) and (WHtR) will be calculated at each visit in which assessed.										
j.	A complete physical examination (including general appearance; eyes, ears, nose, and throat; head and neck; chest and lungs; cardiovascular; abdomen; musculoskeletal; lymphatic; dermatological; neurological systems; mental status; and extremities) will be performed at screening. Brief, symptom-directed physical examinations will be performed on Days 1, 14, 28, 56, 84, and at the EOS and ET Visits.										
